### ***Randomization***

Randomization was conducted in STATA by the research team using the randtreat command. First, 70 kebeles were stratified by woreda, and randomized to either the Cash or No-Cash treatment. Second, 252 villages were stratified by kebele and randomized to either receive or not receive the gPM+ intervention. At each stage, misfits were randomly assigned within each strata, leading to slightly unequal number of villages per treatment arm (See figure 1).

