### ***Empirical approach***

Impacts will be measured immediately following the intervention (endline) and 1-year post-program. We will estimate intent-to-treat (ITT) effects following the assigned treatment using the ANCOVA model when baseline outcome variables are available. We will run probit models for binary outcomes and ordinary least squares models for continuous variables.

*R1: What is the immediate impact of gPM+ on mental health and daily activity?*

To answer the first research question, we will rely on the baseline and endline data. Given that the cash transfer has not yet been distributed, we will combine arms 1 and 3 (no gPM+) and arms 2 and 4 (gPM+) to estimate the following equation:

$$Y_{ihvk}^1 = \beta_0 + \beta_1 gPM_{vk} + \beta_2 X_{ihvk}^0 + \beta_3 Y_{ihvk}^0 + \mu_k + \varepsilon_{ihvk} \quad (\text{EQ 1})$$

Where  $Y_{ihvk}^1$  is the outcome of interest at endline for individual  $i$  from household  $h$  from village  $v$  in kebele  $k$ ; and  $Y_{ihvk}^0$  is the outcome of interest at baseline.  $gPM_{vk}$  is an indicator that equals one if village,  $v$ , was randomized to the gPM+ treatment.  $X_{ihvk}^0$  is a vector of baseline control variables that will include age and sex of the respondent for individual level outcomes. As a robustness check other possible baseline control variables will be included such as enumerator sex and the number and age of children (for childcare outcomes). The specification also includes kebele fixed effects,  $\mu_k$ . Standard errors will be clustered at the village level. We will assess heterogeneity of impacts by sex of the study participant, region, and PHQ-9 score as measured in the screening survey.

*R2-R4: What is the impact of gPM+ on PSNP clients' mental health, daily activity, and economic well-being 1-year after gPM+ sessions end? What is the impact of a one-time lump-sum cash transfer on mental health, daily activity, and economic well-being 1-year after gPM+ sessions end?; What is the added impact of combining gPM+ with a one-time lump sum cash transfer one year after gPM+ sessions end?*

To answer research questions 2-4, we will rely on the baseline and 1-year post-endline data. The main specification we will estimate is the following:

$$Y_{ihvkw}^2 = \beta_0 + \beta_1 Cash_{kw} + \beta_2 gPM_{vkw} + \beta_3 Cash_{kw} * gPM_{vkw} + \beta_4 X_{ihvkw}^0 + \beta_5 Y_{ihvkw}^0 + \gamma_w + \varepsilon_{ihvkw} \quad (\text{EQ 2})$$

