Where  $Y_{ihvkw}^2$  is the outcome of interest at 1-year post-endline for individual  $i$  from household  $h$  from village  $v$  in kebele  $k$  and woreda  $w$ ; and  $Y_{ihvkw}^0$  is the outcome of interest at baseline.  $Cash_{kw}$  is an indicator that equals one if kebele,  $k$ , was randomized to the one-time lump-sum cash treatment;  $gPM_{vkw}$  is an indicator that equals one if village,  $v$ , was randomized to the gPM+ treatment.  $X_{ihvkw}^0$  is a vector of baseline control variables that will include age and sex of the respondent for individual level outcomes. The specification also includes woreda fixed effects,  $\gamma_w$ . As a robustness check we will also run a specification with kebele fixed effects and other possible baseline control variables will be included such as enumerator sex and the number and age of children (for childcare outcomes). Standard errors will be clustered at the village level. We will

assess heterogeneity of impacts by sex of the study participant, region, and PHQ-9 score measured in the screening survey.

In this model,  $\beta_1$  measure the impact of the cash treatment compared to the control group 1-year after the gPM+ sessions ended;  $\beta_2$  the impact of the gPM+ treatment compared to the control group 1-year after the gPM+ sessions ended; and  $\beta_3$  represents the added impact of combining the cash and gPM+ treatment.

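### The kebele-fixed-effects check of EQ 2 cannot cover the cash effect, and village-clustered standard errors are miscalibrated in both EQ 2 and that check

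*Combined protocol and SAP*

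**What the plan says.** The section on randomization in the combined protocol and SAP describes two stages. On cash: "First, 70 kebeles were stratified by woreda, and randomized to either the Cash or No-Cash treatment". On gPM+: "Second, 252 villages were stratified by kebele and randomized to either receive or not receive the gPM+ intervention". Odd-sized strata were handled thus: "At each stage, misfits were randomly assigned within each strata".

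Under Empirical approach, EQ 1 (gPM+ at endline) has kebele effects in its main form: "The specification also includes kebele fixed effects". EQ 2 (one year, research questions 2 to 4) has coefficients β1 for cash, β2 for gPM+ and β3 for their product. Its cash indicator equals one if the kebele "was randomized to the one-time lump-sum cash treatment". Its main form differs from EQ 1: "The specification also includes woreda fixed effects". Kebele effects appear only in the extra run: "As a robustness check we will also run a specification with kebele fixed effects". For both equations: "Standard errors will be clustered at the village level".

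The plan does not say which coefficients the kebele-effects run is meant to check, does not mention that one of them drops out, and gives no reason for the different fixed effects in EQ 1 and EQ 2.

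**The concern.** There are two linked problems.

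First, a regressor that is constant within kebele is an exact linear combination of the kebele dummies. The check is described for EQ 2 as a whole, yet it cannot return β1 or any contrast that includes β1, such as Arm 3 or Arm 4 against Arm 1. Software will drop a column, and which one depends on the ordering. Unless the plan says so beforehand, a printed value could be mistaken for a check of the cash effect.

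Second, village clustering treats villages of one kebele as independent. In the woreda-effects model this errs in opposite directions. Kebele variance largely cancels out of the gPM+ comparison, so the SE for β2 and β3 is too large. It does not cancel out of the cash comparison, so the SE for β1 is too small. In the kebele-effects check the village-clustered SE is too small for β2 and β3. The main model and its check could then disagree on significance only because their SEs err in different directions, and the cash result would carry too high a false-positive risk.

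**Working it through.** **Inputs.** 70 kebeles, 13 woredas, 252 villages (Study setting, Randomization). PHQ-9 row of Table 1: ICC 0.13, correlation r = 0.29, 63 villages per arm, 11 people per village. Cluster-size CV 0.25, alpha 0.05 and power 80% (Power calculations). Alpha is assumed two-sided. Power calculations says the ICC was assessed at kebele level, while Table 1 applies it with villages as clusters. No kebele/village split is given, so a range is used.

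**1. The plan's own figure.** MDE = 2.80 × √[(2/(k·m)) × DE × (1 − r²)], with DE = 1 + ((CV² + 1)m − 1) × ICC.
- PHQ-9: DE = 1 + (1.0625 × 11 − 1) × 0.13 = 2.389. MDE = 2.80 × √[(2/693) × 2.389 × 0.9159] = 0.223, stated as 0.22.
- Productive assets (ICC 0.16, r 0.23, m = 9): DE = 2.37, MDE = 0.249, stated as 0.25.

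**2. Identification.** With kebele dummies, the columns for cash, gPM+, their product and 70 kebeles number 73, and the rank is 72. Without the cash main effect there are 72 columns and the rank is 72, so β2 and β3 are estimable. With woreda dummies there are 16 columns and the rank is 16, so all three are estimable.

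**3. Hand approximation, all of the 0.13 at kebele level.** The residual variance factor is 0.9159 and the village-mean part is 0.87/11 = 0.0791.
- β2, as village clustering sees it: √[2 × 0.9159 × (0.13 + 0.0791)/63] = 0.078.
- β2, with the kebele part cancelling: √[2 × 0.9159 × 0.0791/63] = 0.048.
- β1, true: taking 35 kebeles per side and 252/70/2 = 1.8 non-gPM+ villages per kebele, √[2 × 0.9159 × (0.13 + 0.0791/1.8)/35] = 0.095, against a reported value near 0.078.
- Check, β2 and β3: absorbing 70 kebele means from 252 villages shrinks the village-clustered SE by about √[(252 − 70)/252] = 0.85. This factor does not depend on the ICC.

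**4. Simulation.** 4,000 re-randomisations per scenario with no effect, misfits at random and 11 people in every village. The number of villages per kebele was assumed: 5, 28, 27 and 10 kebeles with 2, 3, 4 and 5 villages. Cells show true SE / mean village-clustered SE / test size at nominal 5%.

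| ICC kebele + village | β1, woreda effects | β2, woreda effects | β2, kebele effects |
|---|---|---|---|
| 0.13 + 0 | 0.099 / 0.073 / 14.9% | 0.053 / 0.072 / 0.9% | 0.050 / 0.042 / 9.8% |
| 0.13 + 0.05 | 0.106 / 0.081 / 13.4% | 0.063 / 0.081 / 1.3% | 0.061 / 0.053 / 9.1% |
| 0.065 + 0.065 | 0.090 / 0.075 / 10.5% | 0.068 / 0.075 / 3.0% | 0.068 / 0.057 / 9.7% |
| 0.02 + 0.11 | 0.081 / 0.076 / 6.5% | 0.074 / 0.076 / 5.0% | 0.075 / 0.065 / 9.3% |

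β3 behaves like β2: size 0.8–4.6% with woreda effects and 8.8–9.4% with kebele effects. A repeat simulation gave a β1 SE of 0.072 against 0.102 (size about 17%) in the first scenario, and 9–11% for the check. Both models are unbiased for β2 and β3; all mean estimates lie within 0.002 SD of zero.

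With kebele clustering, size for β2 and β3 is about 5–6% in either model. For β1 it is 8.1%, 7.8%, 7.4% and 6.0% in the order of the table.

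**5. What the fixed effects alone change.** True SE from woreda to kebele effects, first scenario: β2 0.0529 to 0.0496 (6% lower), β3 0.0748 to 0.0696 (7% lower). Multiplied by 2.80, the MDE goes from 0.148 to 0.139 and from 0.210 to 0.195. At the even split there is practically no gain. At 0.02 + 0.11 the SE rises by about 1% (0.0743 to 0.0752). The repeat run put the largest gain at about 8%.

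**The case against.** The plan never says that the check is for the cash effect. The check works for β2 and β3, and the main form of EQ 2 still identifies β1. This stands: a reader might infer that research question 3 cannot be answered or that the check is void, and neither follows. What is missing is a statement of scope.

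Woreda effects match the first-stage strata and let one model give all three coefficients. This also stands. Because kebele is the stratum for gPM+ and EQ 1 uses kebele effects, a reader might infer that EQ 2 is wrong for β2 and β3 and must be replaced. The documents do not support that: misfits were allocated at random, so the woreda model is unbiased for both. The choice is a preference about precision and consistency.

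A reader might also credit the kebele effects with a large gain in power. Under the plan as written, the effective MDE for β2 is 1.96 × 0.0724 + 0.84 × 0.0529 = 0.186, against 0.139 for kebele effects with kebele clustering. For β3 the figures are 1.96 × 0.1022 + 0.84 × 0.0748 = 0.263, against 0.195. Most of that fall comes from the clustering level. For β2, 0.186 to 0.148 is the SE correction and only 0.148 to 0.139 is the fixed effects.

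Finally, the error for β2 and β3 in the main model is conservative, and it disappears if correlation lies mostly at village level. That is true. It does not excuse the anticonservative test for β1, or the check, which rejects too often under every split tried.

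**Conclusion.** The point holds in two parts. The first needs no assumption: the kebele-effects check covers β2, β3 and β2 + β3 only, and the plan should say so.

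The second is that village clustering is the wrong level for EQ 2 and its check. In the woreda-effects model the size of the error depends on where the correlation lies. With 0.13 at kebele level, which is how Power calculations describes the ICC, test size is about 1% for β2 and β3 and about 15–17% for β1. With 0.02 at kebele and 0.11 at village level it is near 5% for β2 and β3 and 6.5% for β1. In the check it is about 9–11% for β2 and β3 whatever the split.

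These sizes rest on a two-sided 5% test, equal village sizes and the assumed number of villages per kebele, which the documents do not tabulate. Moving β2 and β3 to kebele effects as the main estimate is worth about 0–8% in SE at best, with a loss of about 1% if correlation is mostly at village level.

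**What to change.** - Cluster standard errors by kebele in EQ 2 and in its kebele-effects check. For β1, add a small-sample correction or use randomisation inference, because kebele clustering alone leaves its size at about 6–8%.
- State that the kebele-effects check applies to β2, β3 and β2 + β3 only and that the cash main effect is absorbed.
- Keep woreda effects for every contrast containing β1.
- Optionally, prespecify kebele effects as the main estimate for β2 and β3, in line with EQ 1 and the gPM+ strata. Otherwise give a short reason for woreda effects.

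The cost is wording and code. The reported SE for β1 will grow, in the all-kebele scenario from about 0.073 to 0.089, with the true value at 0.099. If the optional change is made, the components come from two models and will not add up exactly. Kebeles whose villages all fall in one gPM+ arm would add nothing to β2 or β3. The planned probit for binary outcomes would lose kebeles with no variation in the outcome, which matters for savings.

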## **Study design**

The impact of gPM+ will be assessed through a two-stage cluster randomized control trial (cRCT) design. In the first stage, 70 kebeles will be randomized to receive cash or no cash. Randomization of the cash treatment is at the kebele level in order to reduce the risk of spillovers, contamination, and resentment. Randomization of kebeles will be stratified by woreda. In the second stage, within each kebele, up to 6 villages will then be randomized to receive either gPM+ or not receive it, leading to the following four intervention arms across 252 villages:

- Arm-1: control
- Arm-2: gPM+ only

---

[figure not shown]
 Group size will depend on how many individuals are screened in per village

 Although most kebeles have between 3-5 villages, the exact number of villages per kebele varies.

- Arm-3: lump-sum cash transfer only
- Arm-4: lump-sum cash transfer and gPM+.

Study participants in all intervention arms will receive information on locally available mental health services and be PSNP public works clients. Arm 2 will additionally provide study participants with the gPM+ therapy, Arm 3 will additionally provide a one-time lump sum cash transfer, and Arm 4 will provide both the gPM+ and cash transfer.

[figure not shown]
The evaluation will include a baseline survey conducted before implementing the gPM+ or cash transfer intervention (July-August 2022, see Figure 1). The endline survey will be conducted on the same individuals right after the gPM+ intervention but before the cash is rolled out (September-October 2022). A one-year post-intervention survey will be conducted approximately one year after the end-line, approximately one year after the gPM+ sessions and 9 months after the cash transfer (September-October 2023).

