## **Sample and power calculations**

### ***Power calculations***

Power calculations for this study focused on a primary mental health outcome, PHQ-9, and economic outcome, the total value of productive assets. PHQ-9 is a widely used depression diagnostic instrument with scores that range from 0-27. For both outcomes, we drew on data from the endline SPIR I impact evaluation conducted in the same regions of Oromia and Amhara. Given

that SPIR I data did not have data on daily activities, we did not conduct power calculations on this outcome.

We power the study for estimating impacts 1-year after the gPM+ sessions ended across the 4 intervention groups as this requires the largest sample. Power calculations considered the study's design, adjusting for clustering and autocorrelation. Autocorrelations were estimated using the SPIR endline and midline data, while intra-cluster correlations (ICC) were assessed at the kebele level. Power calculations were conducted in STATA using `clustersampsi` command. The desired statistical power was set at 80%, and the desired significance level was set to 0.05. Given that the number of kebeles, villages, and gPM+ group size were pre-determined, we calculate the minimal detectable effect at 1 year post gPM+ for a given number of clusters and cluster size.

We set the number of villages to 252. The number of individuals per village will depend on the number of individuals screened into the study. The max gPM+ group size is 8 women and 8 men per village and the minimum is 3 women and 3 men. On average we expect about 12 individuals per village (6 men and 6 women) at baseline with a coefficient of variation of 0.25. Assuming 8% attrition, rounded to the nearest whole number, the number of individuals per village at 1 year post endline is 11, for a total of 2,772 individuals. For household level economic outcomes, the number of households is estimated differently as two individuals per household (main decision-maker and spouse) are eligible to participate in the study. We expect about 18 percent of the sample to be husband/wife pairs from the same household. This will reduce the number of observations for household-level economic outcomes to 2,218 households.

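### EQ 2 clusters standard errors by village although cash was randomised by kebele, so the standard error of the cash effect is too small whenever outcomes are correlated within kebeles

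*Combined protocol and SAP*

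**What the plan says.** Allocation had two stages. On the first, the Randomization section says: "First, 70 kebeles were stratified by woreda, and randomized to either the Cash or No-Cash treatment". On the second: "Second, 252 villages were stratified by kebele and randomized to either receive or not receive the gPM+ intervention". The Study design section gives the reason for the larger unit: "Randomization of the cash treatment is at the kebele level in order to reduce the risk of spillovers, contamination, and resentment".

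Under Empirical approach, EQ 2 is the main one-year model for research questions 2 to 4. It contains Cash, gPM+, their product, baseline covariates and the baseline outcome. On the area terms: "The specification also includes woreda fixed effects". On the standard errors, in the same words as for EQ 1: "Standard errors will be clustered at the village level". The coefficient β1 is said to "measure the impact of the cash treatment compared to the control group 1-year after the gPM+ sessions ended". β2 is the gPM+ effect against control, and β3 is the added effect of combining the two.

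The only other kebele term planned for EQ 2 is a sensitivity analysis: "As a robustness check we will also run a specification with kebele fixed effects". The Power calculations section adds that "intra-cluster correlations (ICC) were assessed at the kebele level". Kebele clustering, a kebele random effect and randomisation inference appear nowhere.

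**The concern.** Cash takes one value per kebele, so the information on β1 comes from 70 allocated units, not 252. With only woreda effects in the model, whatever the villages of a kebele have in common beyond their woreda remains in the error term. It coincides exactly with the cash assignment. Village clustering treats those villages as independent, which understates the variance of β1.

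The gPM+ contrasts behave differently. gPM+ was allocated within kebeles, so the shared kebele component largely cancels from β2 and β3. Village clustering does not recognise that cancellation, and their standard errors come out too large.

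β1 is the only stated test of research question 3, and Table 2 lists 15 primary outcomes for the one-year round (5 mental health, 4 economic, 6 activity and childcare). A reader of the resulting confidence intervals would have no sign that those for cash were too narrow.

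**Working it through.** **Inputs.** From Randomization: 70 kebeles, 252 villages, cash stratified by woreda, gPM+ stratified by kebele. From Study setting: 13 woredas. From Power calculations and Table 1: cluster-size CV 0.25; PHQ-9 with ICC 0.13, correlation r = 0.29, m = 11 per village; productive assets with ICC 0.16, r = 0.23, m = 9; k = 63 villages per arm; α = 0.05 (two-sided assumed); power 80%. Hence 252/70 = 3.6 villages per kebele, about 1.8 of them without gPM+.

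**The plan's own figures.** MDE = (1.96 + 0.84) × √[2·DE·(1 − r²)/(k·m)], with DE = 1 + [(1 + CV²)m − 1]·ICC.

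- PHQ-9: DE = 1 + (1.0625 × 11 − 1) × 0.13 = 2.389; MDE = 0.2226 (stated 0.22).
- Assets: DE = 1 + (1.0625 × 9 − 1) × 0.16 = 2.370; MDE = 0.2493 (stated 0.25).

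Both reproduce with the village as the independent unit, although the ICC entered was a kebele-level one.

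**Direction, by formula.** If the whole ICC is kebele variance, two village means in one kebele correlate at ρ = ICC/[ICC + (1 − ICC)/m]. For PHQ-9, ρ = 0.13/(0.13 + 0.87/11) = 0.622. With n villages of a kebele contributing to β1, true variance over assumed variance is 1 + (n − 1)ρ. At n = 1.8 the ratio is 1 + 0.8 × 0.622 = 1.497, and the real error rate is 2[1 − Φ(1.96/√1.497)] = 10.9%. At n = 2 it is 12.4%. This shortcut ignores the woreda effects and the unequal numbers of villages, so it was followed by simulation.

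**Simulation under no effect.** EQ 2 was fitted by OLS with woreda effects to data with 70 kebeles, 13 woredas, 252 villages, stratified two-stage assignment and village-size CV 0.25. Runs numbered 1,500 to 10,000 per case; ranges show the spread over repeated simulations. Rejection of β1 at nominal 5% with village-clustered standard errors:

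| Variance share: kebele (after woreda) / village | Rejection |
|---|---|
| 0.13 / 0 (PHQ-9, whole ICC at kebele) | about 15 to 16% |
| 0.16 / 0 (assets, whole ICC at kebele) | about 15 to 16% |
| whole ICC at kebele, plus village variance 0.03 to 0.05 | 13 to 14% |
| 0.065 / 0 (half the ICC absorbed by woreda) | about 12 to 13% |
| 0.065 / 0.05 | 10.5% |
| 0.065 / 0.065 | about 10 to 11% |
| 0.04 / 0.05 | 8.4% |
| 0.03 / 0.10 | 7.4 to 8.6% |
| 0 / 0.13 (no kebele variance) | 4.9 to 6.5% |

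In the first row the mean village-clustered standard error is 0.077 against an actual SD of 0.106, a ratio of 0.726 (27% too small). As a check, 2[1 − Φ(1.96 × 0.726)] = 15.5%, in line with the simulated rate.

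**β2 and β3, same model.** In the first row their standard errors are about 34% too large and rejection is about 1%. With kebele variance 0.02 to 0.04 and village variance 0.05 to 0.10, rejection is about 4 to 5%, close to nominal.

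**After changing the cluster.** Ordinary kebele-clustered standard errors reject β1 in about 8% of null data sets (8.0% PHQ-9, 7.6% assets). There are only 70/13 = 5.4 kebeles per woreda stratum, and the basic sandwich estimator remains liberal. Randomisation inference that re-runs the two-stage assignment (1,686 data sets, 99 re-assignments each) rejected 4.3%.

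**The case against.** The strongest objection concerns size. No document gives a false-positive rate. The plan says the ICCs were assessed by kebele. It does not say whether they are net of woreda differences or whether village variance was separated out. Villages are distinct sites and gPM+ is delivered in village groups, so zero village variance is hard to defend. A reader might infer from the stated ICCs that the error rate simply is 15% or more; the documents do not support that as an unconditional figure. This objection stands, and the size must be given as a range with its assumption.

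Second, part of the excess over 5% is small-sample bias of the sandwich estimator, not the choice of cluster. Plain kebele clustering leaves about 8%, and village clustering can reject slightly above 5% even with no kebele variance. This also stands, and it bears on the fix.

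Third, a reader might infer that the whole one-year analysis is compromised, including research questions 2 and 4. That goes too far. The errors for β2 and β3 are conservative and create no false positives. They shrink as village variance rises. The planned kebele-fixed-effects check also removes the shared kebele component from both. The check does not help β1: cash is constant within a kebele, so the fixed effects absorb it.

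Nor does the point reach EQ 1, where gPM+ was allocated by village and kebele effects are in the model.

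**Conclusion.** The mismatch between allocation and analysis is explicit in the plan and needs no outside assumption. The standard error of β1 in EQ 2 is too small whenever outcomes are correlated within kebeles beyond woreda, and no other planned analysis tests the cash main effect correctly.

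The size is conditional. At nominal 5%, the false-positive rate for β1 is about 15 to 16% if all of the stated ICC (0.13 or 0.16) is kebele variance remaining after woreda effects, and about 8 to 13% under other plausible splits. The inflation essentially vanishes if there is no kebele variance. These figures also assume a particular spread of villages per kebele, because the plan gives only totals and a typical range.

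For β2 and β3 the main specification is conservative: standard errors are up to about 34% too large in the all-kebele case and close to correct when most of the variance lies between villages. This should be corrected before the one-year analysis, because research question 3 rests on β1.

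**What to change.** In EQ 2, cluster at the kebele for all coefficients. Villages nest in kebeles, so this is also valid for β2 and β3. Base the test and confidence interval for β1 on a kebele-level method with small-sample correction, named in advance. CR2 standard errors, a wild cluster bootstrap, or randomisation inference that re-runs the two-stage assignment would each serve; the last is practical because allocation was scripted with randtreat. Which one is chosen matters less than that it works at kebele level and is pre-specified.

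Keep the kebele-fixed-effects specification with village clustering as the check for β2 and β3, and state that it cannot estimate β1. EQ 1 needs no change. Reporting the estimated kebele and village variance components would show where in the range the trial lies.

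The cost is a sentence or two in the plan and a few lines of code, with no new data. The price is wider confidence intervals for cash. With 35 kebeles per cash arm and the whole ICC at kebele level, DE for PHQ-9 is 1 + (1.8 × 11 − 1) × 0.13 = 3.444. The same MDE formula, with 35 × 19.8 = 693 people per group, gives about 0.27 SD for β1 instead of 0.22. For assets it gives about 0.30 instead of 0.25. The Table 1 values should therefore not be presented as applying to the cash contrast.
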